1 BACKGROUND

Turner syndrome (TS) is a condition in which there is loss of the second sex chromosome (either X or Y) and/or abnormality of the second X chromosome in at least one major cell line in a phenotypic female. Features include short stature and primary ovarian insufficiency, accompanied by typical phenotypic traits and a variety of associated cardiac and renal malformations in a minority [1,2].

TS carries a significant morbidity and mortality [3,4]. Long-term health consequences for cardiovascular disease and osteoporosis are particularly important. Problems such as aortic dissection (arising particularly in girls with previously repaired aortic coarctation or bicuspid aortic valve), hypertension, atheroma and increased risk of metabolic syndrome [5,6,7,8,9,] give rise to a marked increase in mortality rate (standardised mortality ratio 3) and a life expectancy 13 years less than the general population, a finding similar to patients with diabetes. However, since TS has a relatively low prevalence, affecting about 1 in 2000 live female births [1], there is little awareness of the condition and its implications.

Appropriate, physiological sex steroid replacement is essential in the optimal management of patients with TS from puberty through to the age of normal menopause. Estrogen induction of puberty is usually required in TS, a retrospective Italian study showing that spontaneous onset of periods (menarche) occurred in only 84 of 522 (16.1%) patients [10]. Puberty is a highly important process both physically and psychologically. Over 50% bone mineral accrual occurs during puberty & the early post-pubertal years [11]. Moreover timely pubertal induction is important for self-esteem, psychosexual development and quality of life.

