The European Society of Human Reproduction and Embryology (ESHRE) has developed clinical practice guidelines for the management of women with primary ovarian insufficiency (POI) [12]. Clinical practice guidelines for the care of girls and women with TS were published after the International Turner Syndrome Meeting in Cincinnati [13]. Matthews and colleagues from the United Kingdom (UK) have described a consensus from the British Society for Paediatric Endocrinology and Diabetes on hormone supplementation for pubertal induction in girls with POI [14]. Christin-Maître published a review on the use of hormone replacement in females with endocrine disorders [15]. However, the Cincinnati guidelines do not cover pubertal induction in depth, and the other papers mentioned do not deal specifically with TS.

While transdermal estrogen treatment has theoretical advantages over oral treatment and has been used in Sweden for decades (16), the evidence for any superiority is lacking. Matthews et al write, "There is a real paucity of carefully constructed, randomised controlled clinical trials in girls undergoing induction of puberty. The evidence base is derived mainly from expert experience, a small number of observational studies and very few controlled trials on small study populations. In addition, studies of treatment acceptability and patient adherence are lacking" [14]. Thus, while transdermal delivery of physiological 17β -estradiol estrogen may be superior to oral ethinylestradiol in terms of cardiac, bone and uterine health in POI [17,18,19], adequately powered studies are needed to address these as well as other elements such as growth during pubertal induction, adherence and acceptability [20].

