3.2 Outcomes

The primary outcome measure is height gain in cm during the pubertal induction period, since this can be accurately determined in the context of an international framework. Secondary outcome measures include final adult height, systolic blood pressure, aortic root diameter, uterine size and shape, bone mineral density, adherence and dropout rate.

Table 1 Outcome measures to be analysed at the end of pubertal induction in girls with Turner syndrome using either an oral (see Tables 2a and 2b) or transdermal (see Tables 3a and 3b) 17- β estradiol regimen approved by the Turner Syndrome Working Group of ESPE.

Induction period is normally 3 years (plus 6 months for very short girls), exceptionally 2 years for girls presenting late (e.g. >14 years), minimum follow up is during induction period but where possible, follow up is to final adult height.

Primary outcome measure

Pubertal height gain, i.e. increase in height in centimetres during the (usually) 3-year pubertal induction period

Secondary outcome measures

- Final adult height in centimetres & population-specific SDS
- Change in population-specific height SDS between start and end of pubertal induction
- Breast development (clinical assessment)
 - Tanner B4-5 reached
 - Satisfactory breast shape (ie not tubular, no overdevelopment of areolae) according to attending clinician (graded as satisfactory or unsatisfactory)
- Cardiovascular health
 - Systolic & diastolic blood pressure at the end of induction (lowest of three readings or mean values if recorded by ambulatory 24-hour blood pressure monitoring
 - Change in aortic root diameter and aortic size index between start and completion of induction
- Patient satisfaction; adherence/compliance with treatment
 - Percentage drop-outs from either regimen
 - Average of good, reasonable and poor rating with adherence during pubertal induction (3 years ± X months)
 - Patient satisfaction with shape and size of breast (scoring 1-5 where 5=best)
 - Patient satisfaction with mode of administration (scoring 1-5 where 5=best)
- Uterine health and sex hormone profile at the end of induction
 - Uterine length and volume, endometrial thickness
 - Uterine shape and fundo-cervical ratio
 - LH and FSH
 - Serum 17-β estradiol

- Skeletal age and bone health
 - Change in bone age/chronological age per year
 - Change in size-adjusted whole body lumbar spine and hip bone mineral areal density (BMAD) (z-score) before and after induction
- Metabolic profile

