4.5 Data collection before and during pubertal induction

Table 4 shows the recommended information to be collected before, during and at the end of pubertal induction, and until adult height, i.e. height velocity < 2 cm/year.

TABLE 4 Recommended measurements before, during and at the end of pubertal induction with either transdermal or oral 17-β
estradiol grouped according to priority – essential and desirable.

Variable	Before induction (± 6 months)		End of Years 1 & 2	End of Year 3	Comment	
ESSENTIAL	(2 o montho)	visito				
Karyotype	X				From time of diagnosis	
Auxology Height (cm)	x	x	x	х		
Weight (kg)	X	Х	X	Х	 Previous growth data will be requested, to enable calculation of a) height velocity, using 12 (±1) month interval, during previous year; and GH responsiveness – derived from height/weight status one year prior to, at the start of, and one year after starting GH. 	
Height velocity (cm/yr)	X		X	Х		
Measured parental heights (where available)	X					
Breast and pubic hair stage (1-5)	X	Х	X	Х		
Systolic & diastolic blood pressure (mm Hg)	Х	Х	Х	Х	Lowest of three consecutive readings using Dinamap V100 or similar device	
Adherence to treatment		X	Х	Х	Scored according to estrogen doses missed per month as good (≤ 2) moderate (≤ 4) and poor (> 4)	
Adverse events/illness		Х	Х	Х	All adverse events (e.g. injury, intercurrent infection) irrespective of relevance to growth and puberty	
FSH, LH	X			Х		
Free T4 and TSH	Х			Х		
Liver function	Х		Х	Х		
HbA1c	Х			Х		
Concurrent treatment	Х	Х	Х	Х	GH, L-T4, Oxandrolone	
DESIRABLE	1					
Final adult height					Measurement once height velocity < 2cm/year	
Bone age	Х		Х	Х	Assessed using 'BoneXpert', where available	
Sitting height	X	X	Х	Х		
Echocardiography	X			Х	Including measurement of aortic size index	
Pelvic ultrasound	Х		X	Х	Uterine length, shape and volume, endometrial thickness	
DXA BMC	Х			Х	Hip and lumbar spine z-score Total body BMD	
Fasting lipid profile	Х			Х	Cholesterol, triglycerides, low and high-density lipoproteins	
Coagulation studies	X			Х		
Serum estradiol	X			Х	Beginning of Year 4 (see Table 2)	
Serum IGF-I	X		Х	Х	Keep +1.5 -2.5 SD of reference range	
24h continuous ambulatory blood pressure	X			Х		
Fasting blood glucose and insulin	Х			Х		

Abbreviations

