FSH = follicle stimulating hormone; LH = luteinising hormone; fT4 = free thyroxine; TSH = thyroid stimulating hormone; DXA = dual X-ray absorptiometry; BMC = bone mineral content; BMD = bone mineral density; GH = growth hormone; L-T4 = levo-thyroxine. *4-monthly visits are recommended; however 3-6 monthly may be more suitable for some participating centres.

It should be noted that measurements such as height, weight, pubertal stage and blood pressure are marked as 'essential' and are within the scope of any paediatric service caring for girls with TS. By contrast, 'desirable' measures should be undertaken at the clinician's discretion, and take account of the resources available in the participating centre.

Since height gain during induction is the agreed primary outcome measure, previous height and weight data from one year before, at the time of and one year after the start of GH treatment and at least yearly thereafter, together with GH dose and possible oxandrolone treatment, are required to assess GH responsiveness [29,30].

Karyotype (normally available from time of diagnosis) is essential information.

At each visit, measurement of height, weight, blood pressure, pubertal stage, adherence (scored according to the number of estrogen doses estimated by the family to have been missed per month), recording of adverse events, and concurrent treatment are required.

Note that the family will be asked at each visit about **any** adverse events including minor injury, intercurrent infection, middle ear problems and gastrointestinal symptoms, and summarised at the end of each year by the clinician.

Annual biochemistry for thyroid function and liver function, FSH, LH and estradiol levels will be carried out as part of normal clinical practice.

Echocardiogram to define the anatomy of the heart and great vessels, with measurement of aortic root diameter at the annulus, and aortic size index (aortic root diameter divided by body surface area), is recommended before and at the end of induction.

Pelvic ultrasound, measuring uterine length, fundo-cervical ratio, uterine shape (infantile, cylindrical and pubertal) and endometrial thickness are also recommended before and after induction.

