6.1.2 Exclusion criteria

There are no formal exclusion criteria. However, note will be taken in the analysis of patients with accompanying health problems such as hypothyroidism, coeliac disease and inflammatory bowel disease, all of which have an increased prevalence in TS. Moreover, problems with adherence/compliance will also be taken into account when analysing the data.

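### Table 4 does not ask for blood-pressure-lowering drugs or for known hypertension and cardiac lesions at baseline, so the blood pressure comparison cannot reliably take them into account

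*Protocol*

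**What the plan says.** **Outcomes.** Protocol section 3.2, Table 1, lists systolic and diastolic pressure at the end of induction as secondary outcomes, together with "Change in aortic root diameter and aortic size index between start and completion of induction".

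**Who enters and how regimen is set.** Section 6.1.2 sets no formal exclusions. Section 4.1 describes an open study in which family and clinician choose the regimen. Section 1 counts among the important problems of Turner syndrome "aortic dissection (arising particularly in girls with previously repaired aortic coarctation or bicuspid aortic valve), hypertension".

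**What is collected.** In section 4.5, Table 4:
- Concurrent treatment is essential at every time point, with the comment "GH, L-T4, Oxandrolone".
- Blood pressure is essential at every time point, including before induction.
- Adverse events/illness is essential at visits and at the end of each year, but has no mark in the before-induction column. Its comment reads "All adverse events (e.g. injury, intercurrent infection) irrespective of relevance to growth and puberty".
- Echocardiography and 24-hour ambulatory pressure are in the lower tier, of which the text says "desirable' measures should be undertaken at the clinician's discretion, and take account of the resources available in the participating centre".

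The text after the table says that at each visit "recording of adverse events, and concurrent treatment are required", with no drug class named. It also says that the echocardiogram, recommended before and at the end of induction, defines the anatomy of the heart and great vessels.

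**What the analysis will use.** Section 4.6 plans propensity score matching, with growth-related factors as examples, and a causal diagram to find the confounders for each outcome, followed by regression. Section 6.1.2 adds that the analysis will note "accompanying health problems such as hypothyroidism, coeliac disease and inflammatory bowel disease".

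**The concern.** The end-of-induction pressure is a raw value that drug treatment alters directly. A girl whose hypertension is controlled by drugs counts as a good result for her regimen. Because regimen is chosen rather than assigned, hypertension, cardiac lesions and their treatment may be unevenly spread between the arms. A causal diagram for blood pressure would be expected to include known hypertension and cardiac disease. Regression cannot adjust for a variable that was not collected.

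At stake is whether a difference in blood pressure between the routes, or its absence, can be attributed to the route. Blood pressure is named in the research question (section 3), so the result will be read.

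**Working it through.** The point is about data collection, so the main check sets the passages side by side. The arithmetic only scales a possible bias.

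**1. Plan's own figure.** The protocol gives no figure for blood pressure. Its only calculation is for height gain (section 6.2): n = 21/f², with f = 2.5/3.5, gives 41.16, hence 42 per arm, doubled to 84. This reproduces and is not in dispute. The 84 is used below as the arm size.

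**2. Is antihypertensive use captured?** The Table 4 comment names three treatments with no marker that they are examples, whereas the adverse-events row has one. The running text asks for concurrent treatment in general. Antihypertensives are named nowhere in the protocol. Some centres may record them and others may not.

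**3. Is known hypertension or a cardiac lesion captured at baseline?**
- No essential Table 4 item asks for either.
- The adverse-events/illness row starts after induction begins, so it does not collect pre-existing conditions.
- The accompanying health problems of section 6.1.2 have no matching row in Table 4.
- An echocardiogram would show a lesion, but it is discretionary and, under section 4.5, not a condition of participation. Blood pressure is collected in every girl; lesion status is available only in those with an echo.

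**4. Does baseline blood pressure close the gap?** Only in part. It captures untreated hypertension at entry. A girl already controlled on drugs has a normal value at both ends. A girl who starts drugs during induction shows a fall that is credited to her regimen.

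**5. The aortic outcome.** A girl contributes a change in aortic root only if she has an echo at both time points, and that echo defines anatomy. Lesion status is therefore obtainable for the girls in this comparison. Surgical history and antihypertensive use are not asked for.

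**6. Possible size for systolic pressure.** Neither input below is in the protocol; both are assumptions.

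Shift in the difference between arm means = difference in treated proportion × drug effect.
- Low: 0.05 × 8 = 0.4 mmHg
- High: 0.20 × 10 = 2.0 mmHg

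To put this against chance, assume further an SD of 10 mmHg, 84 per arm and no true difference. The standard error is 10 × √(2/84) = 1.543 mmHg. The two-sided false-positive rate is Φ(b/1.543 − 1.96) + Φ(−b/1.543 − 1.96), where b is the shift.

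| Shift b (mmHg) | b/1.543 | False-positive rate (nominal 5%) |
|---|---|---|
| 0.4 | 0.259 | 0.0445 + 0.0132 = 5.8% |
| 1.0 | 0.648 | 0.0948 + 0.0046 = 9.9% |
| 2.0 | 1.296 | 0.2534 + 0.0006 = 25.4% |

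**The case against.** The strongest reply is that the protocol is less restrictive than the table cell suggests. Table 4 is headed as recommended measurements, the text requires concurrent treatment without limit, and the health problems in section 6.1.2 are introduced as examples, so hypertension or a repaired coarctation would fit. Hypertension arising during induction could be entered under adverse events/illness. Baseline pressure is essential in every girl. Detailed form fields and covariate lists often sit in other documents. All of this stands, and it rules out saying that the protocol forbids or excludes these data. It does not show that they will be collected consistently: the one place that tells centres which treatments to enter names three, and none lowers blood pressure.

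Three stronger readings are tempting and are not supported.
- **That the aortic comparison cannot be separated from cardiac disease.** The paired echocardiograms supply lesion status for the girls who enter that comparison.
- **That the protocol itself gives grounds for steering girls with cardiac risk to patches.** Section 1 says that transdermal estradiol "may be superior to oral ethinylestradiol in terms of cardiac, bone and uterine health", but the oral drug in this study is 17β-estradiol, and the same section says that evidence of superiority is lacking. Uneven choice by cardiac risk is possible, not documented.
- **That missing data could never be recovered.** The protocol does not limit transmission to the Table 4 items, and study numbers with identities held by the enrolling physician leave site queries possible. They would come years after the visits.

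The size is also open to challenge. It rests wholly on assumed inputs, and the protocol gives no rate of antihypertensive use in this age group.

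**Conclusion.** The point holds for blood pressure. Followed as written, the plan yields a comparison of end-of-induction pressure that cannot reliably be adjusted for, or read in the light of, antihypertensive treatment, nor adjusted for cardiac lesions in girls without an echo. For the aortic outcome only surgical history and antihypertensive use are missing.

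The size of any bias is unknown. The 0.4-2.0 mmHg range requires both the assumed drug effect and the assumed imbalance; the false-positive rates also require the assumed SD. If use is rare or balanced, the bias is small. Only secondary outcomes are touched; height gain and its sample size are unaffected. This is a worthwhile, inexpensive improvement, not a flaw in the main comparison.

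**What to change.** 1. In Table 4, add blood-pressure-lowering drugs to the essential concurrent-treatment row.
2. Add one essential baseline item, taken from the existing clinical record: known hypertension, bicuspid aortic valve, coarctation, or aortic surgery (yes/no for each).
3. In section 4.6, name these baseline items as candidate confounders in the causal diagrams for the blood pressure and aortic outcomes.
4. Report blood pressure with treated girls identified, for example with hypertensive or on treatment as a companion outcome. Do not adjust for treatment started during induction: it follows the choice of regimen and may be a consequence of it.

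The cost is a few form fields, slightly more data entry per visit and a short addition to the analysis text. No new test or visit is needed, and clinical management is unchanged.

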Number of patients in each group in whom all parameters are normal at the end of induction for:

- Liver function
- Cholesterol, triglycerides, low and high density lipoproteins, apoprotein A1, B and A1:B ratio
- Fasting glucose and insulin (HOMA)

4 STUDY DESIGN and METHODS of DATA COLLECTION AND DATA ANALYIS

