	Not applicable	50 – 75 (-100) μg/24h (Often ~1 ug/kg/24h)		Patch continuously attached to the skin. Apply whole patch three times weekly, changing after 2 days Serum sample for estradiol target to be drawn in the morning after the previous evening's
			· · · ·	dose, target range 150–450 pmol/L

*Girls in whom low final height is anticipated may receive an extra 6 months of the Year 1 dose **Year 4 suggests a post-induction dose

**Serum estradiol sample to be drawn early of Year 4 in the morning using the post-induction dose and a new patch applied the evening before, target range 150–450 pmol/L [25]

Table 3b Two-year transdermal 17β -estradiol regimen for pubertal induction in girls presenting late (e.g. >14 years) and judged by clinician and family to require a shorter induction period. Year 3 corresponds to suggested post-induction dose. The dose at the beginning of each year is calculated according to body weight.

	Weight (kg)	50 µg patch	25 µg patch	Duration of treatment,	
				Instructions	
Year 1 (0-	-6 months)				
	< 40 kg	1/16 of patch (3.1 µg)	1/8 of patch (3.1 µg)	10-12 hours (overnight, to mimic the normal diurnal variation)	
	40-55	1/12 of patch (4.2 μg)	1/6 of patch (4.2 μg)		
	>55	1/8 of patch (6.2 µg)	¼ patch (6.2 µg)		
Year 1 (7-	-12 months)				
	< 40 kg	1/8 of patch (6.2 μg)	1/4 of patch (6.2 µg)	10-12 hours (overnight)	
	40-55	1/6 of patch (8.3 µg)	1/3 patch (8.3 μg)		
	>55	¼ of patch (12.5 μg)	½ patch (12.5 µg)		
Year 2					
	< 50 kg	1/3 of patch (16.7 μg)	2/3 of patch (16.7 μg)	Cut the desired dose into two halves; attach both parts to the skin in the evening.	
	50-65	3/8 patch (18.8 µg)	3/4 patch (18.8 μg)	After 10-12 hours (overnight) remove one part keep the second part during the day. Remove	
	>65	1/2 of patch (25 µg)	1 patch (25 µg)	second part in the evening, before evening application of a two further half patches. This results in a diurnal dose variation, with higher dose nighttime.	
Year 3**	Post-inductio				
	Not applicable	50 – 75 (-100) μg/24h (Often ~1 ug/kg/24h)		Patch continuously attached to the skin. Apply whole patch three times weekly, changing after 2 days Serum sample for estradiol target to be drawn in the morning after the previous evening's	
Sirls in wh	hom low final h			dose, target range 150–450 pmol/L e an extra 6 months of the Year 1 dose	

*Girls in whom low final height is anticipated may receive an extra 6 months of the Year 1 dose **Year 4 suggests a post-induction dose

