Dual X-ray absorptiometry (DXA), with measurement of bone mineral density at the lumbar spine and hip is recommended before and at the end of induction, the measurements being converted to standard deviation scores. Due to different machines in different centres, with no possibility to harmonise the data from the range of equipment, the patients' individual change in bone mineral density standard deviation score will be the used variable in the study.

As stated above, these investigations depend on local availability and are not prerequisites for participation in the study.

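### The bone outcome is defined in two ways, and the satisfaction scores, breast-shape rating and apoproteins are outcomes with no listed collection point

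*Protocol*

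**What the plan says.** **Bone.** Table 1 (section 3.2) gives the outcome as "Change in size-adjusted whole body lumbar spine and hip bone mineral areal density (BMAD) (z-score) before and after induction". Section 4.5 describes DXA "with measurement of bone mineral density at the lumbar spine and hip is recommended before and at the end of induction", converted to standard deviation scores. Because scanners cannot be harmonised between centres, it concludes that each patient's "individual change in bone mineral density standard deviation score will be the used variable in the study". The DXA row of Table 4, in the desirable group, reads "Hip and lumbar spine z-score Total body BMD".

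**Satisfaction and breast shape.** Table 1 lists two patient scores from 1 to 5. One is for breast shape and size; the other is "Patient satisfaction with mode of administration (scoring 1-5 where 5=best"). It also lists a clinician grading of breast shape as satisfactory or unsatisfactory. Table 4 has no row for any of the three. Its only breast item is the stage from 1 to 5. The section 4.5 list of what is recorded at each visit covers height, weight, blood pressure, pubertal stage, adherence, adverse events and concurrent treatment.

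**Apoproteins.** The lipid line of Table 1 includes "apoprotein A1, B and A1:B ratio". The lipid row of Table 4 stops at cholesterol, triglycerides and low- and high-density lipoproteins.

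**The concern.** A protocol may leave much to the analysis plan, but here it states the bone variable twice and the statements differ. Areal density rises with bone size as well as with true density. The primary hypothesis is that the arms differ in height gain, so an unadjusted bone measure would carry part of any height effect into the bone comparison and favour the taller arm. The reason section 4.5 gives for using SDS change is differences between machines, which does nothing about bone size.

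The second matter is one of collection. A centre that follows Table 4 and section 4.5 will not record satisfaction, breast shape or apoproteins. Satisfaction during induction is hard or impossible to recover later, and no analysis plan can supply it. Patient satisfaction is a named secondary outcome in the synopsis.

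**Working it through.** **Design figures.** Section 6.2 takes a difference of 2.5 cm and an SD of 3.5 cm, so f = 2.5/3.5 = 0.714. The Lehr formula gives n = 21/f² = 41.2 (41.7 with f rounded to 0.71), which rounds up to the stated 42 per arm and is doubled to 84. This reproduces. Power for height gain is 90.5% at 42 and 99.6% at 84 per arm. The point here does not touch these figures; 2.5 cm is used below only as the protocol's own height difference.

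**Outcome list against collection list.**

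| Item | Table 1 | Table 4 | Section 4.5 text |
|---|---|---|---|
| Bone variable | size-adjusted z-score, change | z-score and total body density, no size adjustment named | density SDS, change, no size adjustment named |
| Bone sites | whole body, lumbar spine, hip | hip, lumbar spine, total body | lumbar spine, hip |
| Satisfaction with breast, 1-5 | yes | no row | not mentioned |
| Satisfaction with mode of administration, 1-5 | yes | no row | not mentioned |
| Clinician grading of breast shape | yes | no row (stage only) | not mentioned (pubertal stage only) |
| Apoproteins | yes | not in lipid row | not mentioned |

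**Size of a possible body-size effect on bone.** The protocol gives no density figures, so these inputs are assumptions:
- For bones of similar shape and equal true density, mineral content scales with length cubed and projected area with length squared, so areal density scales with length. It is taken as proportional to height.
- Height at the end of induction (H) is 140 to 150 cm.
- The reference SD of areal density is 10 to 15% of its mean (CV 0.10 to 0.15).
- The arms have equal height at the start.

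Spurious difference in SDS change = (2.5/H)/CV.
- Largest: 2.5/140/0.10 = 0.18.
- Smallest: 2.5/150/0.15 = 0.11.

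**Chance of a false bone finding.** Assume an SD of SDS change of 0.5 to 1.0, a two-sided 5% test and n per arm. The standard error is SD × √(2/n).
- n = 84, smallest case: 1.0 × √(2/84) = 0.154, and 0.111/0.154 = 0.72 standard errors. The test would be significant about 11% of the time.
- n = 84, largest case: 0.5 × √(2/84) = 0.077, and 0.179/0.077 = 2.3 standard errors. The test would be significant about 64% of the time.
- n = 42, for instance if half the girls have DXA, which is only a desirable item: about 8% to 37%.

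With no height difference between arms, the spurious shift is zero and the rate stays at 5%.

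**Would the planned adjustment remove it?** The examples of confounders in section 4.6 include height at the start of induction but not height gain. Height gain arises after treatment starts, so it is not a baseline confounder. The remedy belongs in the outcome measure.

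**The case against.** **Bone.** Section 4.5 never says that density is unadjusted. A size-adjusted z-score is also an SDS, and the sentence is there to explain why change in SDS replaces raw values. The DXA row of Table 4 is labelled with bone mineral content, and height is an essential item, so some of what size adjustment needs is already named. This stands in part. A reader might infer that the bone results will be biased by height, but the text does not support that. Bias needs both an unadjusted reading and a real difference in height gain. What remains is that the size qualifier in Table 1 is missing from the two places that tell centres and analysts what to use.

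**Acceptability.** A reader might infer that acceptability cannot be answered. It can in part: the synopsis glosses it as adherence, adherence is an essential item at every visit, dropout is recorded centrally (section 7.5), and both are analysed under section 4.6. Only the satisfaction scores lack a listed source.

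**Collection.** Table 4 gives recommended measurements and the appendices are still to be completed, so these items are not listed for collection, which is weaker than never collected. The Table 1 caption does place its outcomes at the end of induction. That gives an analysis time but no instruction to record.

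**Metabolic count.** "Number of patients in each group in whom all parameters are normal at the end of induction for" might be taken as one composite without a usable denominator. It introduces three separate lines and can be read as one count per panel. Liver function is essential, and the optional status of the other tests is openly stated. Only the missing apoproteins are a mismatch.

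**Estradiol.** The Table 3a footnote has the "Serum estradiol sample to be drawn early of Year 4 in the morning using the post-induction dose", and a reader might infer that the arms are sampled on different footings. The documents do not show this: Table 2a also recommends a morning sample at the beginning of Year 4 for the oral arm, and section 4.5 foresees annual estradiol levels. At most, Table 1 (end of induction) and the Table 4 comment (beginning of Year 4) leave unclear which sample is the outcome.

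**Conclusion.** The point holds in a limited form. The bone outcome is stated in two ways, differing in size adjustment and in sites. Following section 4.5 literally would leave the bone comparison open to a shift of about 0.11 to 0.18 SD if the arms differ by 2.5 cm. That size rests wholly on the stated scaling, height and reference-SD assumptions, and it applies only if density is left unadjusted and height gain differs. Four Table 1 items (two satisfaction scores, the breast-shape rating and the apoproteins) are not listed for collection, so the satisfaction part of acceptability would have no data from centres that follow the schedule. All of this concerns secondary outcomes; the primary outcome and the sample size are unaffected. It should be corrected before enrolment, because the satisfaction scores cannot readily be obtained afterwards.

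**What to change.** - Name change in the size-adjusted z-score as the single bone variable, with the same sites, in Table 1, Table 4 and section 4.5. Record the DXA bone area and mineral content needed to derive it.
- Add both 1-5 satisfaction scores and the breast-shape rating to Table 4, at the end of induction and at drop-out.
- List the apoproteins in the lipid row of Table 4, or remove them from Table 1.
- State which estradiol sample is the end-of-induction outcome, so that Table 1 and the Table 4 comment agree.

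The cost is table wording, two short questions, one clinician rating, and DXA fields from scans already being done. If the apoproteins are kept, centres able to run them bear one added assay.
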